Patients whose hypersomnia is judged to be due to or primarily associated with a medical or psychiatric disease, e.g., Parkinson's disease, myotonic dystrophy, severe depression, will be excluded. However, patients with a diagnosis of narcolepsy type 2 or idiopathic hypersomnia who have medical or psychiatric comorbidities not thought to be causal to daytime sleepiness will not be excluded. Drs. [name] and [name], board-certified neurologists, will assess for the relationship between any medical comorbidities and hypersomnolence. [name], a clinical psychologist, will assess for the relationship between any psychiatric comorbidities and hypersomnolence.

1) The primary outcome will be change in sleepiness from baseline, as measured by the Epworth Sleepiness Scale at baseline and week 12. Secondary outcomes will be sleep inertia and cognitive dysfunction. Current literature does not support the use of a particular, validated instrument for either of these measures, which have historically not been assessed in RCTs performed in participants with the central disorders of hypersomnolence. However, stakeholders have identified these two clinical features as particularly problematic, and therefore it is important to include measures of change of these symptoms in pragmatic clinical trials. The patient global impression of change (PGI-C) is a validated tool to assess change in symptoms (26), which has been used for the assessment of a wide variety of

sleep and non-sleep symptoms in clinical trials (27-31). We will assess three separate PGI-C features: sleepiness, sleep inertia (defined for participants as "difficulty waking up and getting out of bed in the morning because of sleepiness"), and cognitive dysfunction (defined for participants as "difficulty with thinking, problems with attention or concentration, and/or 'brain fog'"). For participants taken off meds, they will be asked to "compared to the medication (or medications) you were taking just before your started the study, which treatment did you prefer overall". Measures will be collected at baseline, week 4, week 8, and week 12. Week 4 and 8 measures will be collected remotely from patients using the electronic, HIPAA-compliant REDCap data collection system (32). Baseline and week 12 measures will be collected in a face-to-face visit, mimicking the frequency of follow up in routine clinical practice.

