APPENDIX 1. SCHEDULE OF STUDY VISITS

	VISIT 1	VISIT 2 – SLEEP STUDY	VISIT 3	VISIT 4	VISIT 5
Informed Consent	X				
Medical History	X				
Study Inclusion/Exclusion	X				
Concomitant Medication Review	X	X	X	X	X
Wean off current wake- promoting medicines	X				
Adverse Experiences		X	X	X	X
Participant Payment	X				X
PSG/MSLT sleep study		X			
Sleepy Packet	X				
Sleep Inertia Questionnaire	X	X	X	X	X
Epworth Severity Scale	X	X	X	X	X
CGI- Baseline Questionnaire	X	X	X	X	X
CGI- Sleep Inertia Questionnaire	X	X	X	X	X
CGI- Sleepiness Questionnaire	X	X	X	X	X
CGI- Cognitive Dysfunction Questionnaire	X	X	X	X	X
Treatment Questionnaire	X	-	X	X	X
Treatment Comparison Questionnaire	X	-	X	X	X
Study Drug Titration Reviewed	X				
Randomization	X	OR X			
Dispensing or Administration of Study Drug	X	OR X	X	X	
Counting of Returned Study Drug			X	X	X

Informed Consent Process

Consent will be obtained in-person from a study PI, co-I, or coordinator. Comprehension will be ensured by allowing ample time for questions and discussion and verbally reviewing the information with the subject in addition to reviewing the written consent form. The discussion will take place at the Emory Sleep Center.

Compensation

Participants will be compensated \$25 for visit 1 (enrollment) and \$25.00 for the week 12 study visit (visit 5), for a total of \$50.

Statistical Analysis

Sample size will be 22 in each group. This sample size is sufficient to demonstrate a reduction in ESS of 4 points with amphetamine salts, assuming a standard deviation of change from baseline of 6.2 (35). This is

a conservative, but clinically significant, change in Epworth, compared to the observed change from baseline of 5.3 points in clinical trials of modafinil [weighted average from (15, 35, 36)]. This sample size provides 82.8% power to find a moderately large effect size for amphetamine salts. For non-inferiority, we will use a responder definition of those achieving a 25% reduction in ESS, a data-driven minimal clinically significant change in patients with narcolepsy (29). Assuming 80% of participants meet this threshold, 22 participants per group will provide 80% power to a non-inferiority limit of 30% (37, 38).

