Intention-to-treat analyses will be performed, using last observation carried forward in the event of participant drop-out. The change in ESS at week 12 from baseline will be compared between the two treatment groups via t-test (compared for unequal variances if necessary) and will be evaluated on a hypothesis of non-inferiority. Similar analyses will be performed on secondary outcomes, considering the proportion of responders in each treatment arm who rate themselves "much improved" or "very much improved". Categorical outcomes, including these PGI-C proportions and adverse events, will be compared using Chisquare or Fisher exact test. Exploratory analyses will evaluate response at week 4 and week 8 between the two medications groups, to determine if there is a difference in time to symptom control.

Considering each medication separately, predictors of response will be assessed using logistic regression. The main predictor of interest will be hypersomnia diagnosis, i.e., narcolepsy type 2 or idiopathic hypersomnia. Other predictors, to be considered in separate, exploratory regression models, include: MSLT mean sleep latency, MSLT number of SOREMs, sex/gender, baseline ESS, age, and comorbidities. Significant predictors in univariate models will be combined in a multivariate model. Although the investigative team has extensive clinical trial and statistical experience, additional statistical consultation will be provided as needed through Emory's CTSA consultation program.

Data Safety Monitoring and Reporting

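### The sample-size and analysis paragraphs name different non-inferiority analyses, so the stated 80% power is not the power of the t-test that carries the hypothesis

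*Combined protocol and SAP*

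**What the plan says.** Study Design & Methods defines the primary outcome as a change score: "The primary outcome will be change in sleepiness from baseline, as measured by the Epworth Sleepiness Scale at baseline and week 12".

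The sample-size paragraph of the Statistical Analysis section sets the size ("Sample size will be 22 in each group") and turns to non-inferiority after a separate power statement (82.8%) about an effect of amphetamine salts. There it uses a proportion: "For non-inferiority, we will use a responder definition of those achieving a 25% reduction in ESS". The power claim follows: "Assuming 80% of participants meet this threshold, 22 participants per group will provide 80% power to a non-inferiority limit of 30" percent. A reference is attached to the 25% threshold, and a binary-outcome calculator and a methods paper to the power claim. The 80% rate has no source of its own.

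The next paragraph of the same section gives the analysis. Change in ESS at week 12 is compared between arms "via t-test (compared for unequal variances if necessary) and will be evaluated on a hypothesis of non-inferiority". For secondary outcomes it describes "considering the proportion of responders in each treatment arm who rate themselves" as being in the top two PGI-C improvement categories. That is the only responder definition in the paragraph.

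The documents give no alpha, no sidedness and no non-inferiority margin in ESS points.

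**The concern.** A non-inferiority conclusion needs one endpoint, one margin on that endpoint's scale, and one error rate. Here the margin and power belong to a proportion, while the hypothesis is attached to a difference in means. Followed literally, the analysis paragraph calls for a non-inferiority t-test with nothing to compare the confidence limit against, and the sample-size paragraph powers a comparison that the analysis paragraph never lists.

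Two things are at stake. The 80% could be carried over to the t-test, for which no power is given. And the margin, or even the choice between the two tests, could end up being settled after the data are known.

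**Working it through.** **Inputs from the plan.** 22 per group; responder rate 80%, taken as equal in both arms; limit 30%, read as an absolute difference; "assuming a standard deviation of change from baseline of 6.2"; and, for scale, "compared to the observed change from baseline of 5.3 points in clinical trials of modafinil".

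**Assumptions added here.** One-sided alpha of 5% or 2.5%, because none is stated; SD 6.2 in both arms; no true difference between the drugs.

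**1. Reproducing the plan's figure (responder comparison).**

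- Standard error of the difference: √(2 × 0.8 × 0.2 / 22) = 0.1206.
- Power = Φ(0.30 / 0.1206 − z) = Φ(2.487 − z).
- One-sided 5% (z = 1.645): Φ(0.842) = 80.0%. Required n = (1.645 + 0.842)² × 2 × 0.8 × 0.2 / 0.3² = 21.98, so 22 per group.
- One-sided 2.5% (z = 1.960): Φ(0.527) = 70.1%. Required n = 27.91, so 28 per group.
- One-sided 10%: 88.6%, with 17 per group required.

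Of these three levels only one-sided 5% returns the plan's numbers. Other variance methods stay close: at one-sided 5%, exact enumeration of the Wald-limit rule gives 81.8% and a null-restricted variance gives 78.4%.

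**2. Power of the t-test in the analysis paragraph.** The standard error is 6.2 × √(2/22) = 1.869 points. Power comes from the noncentral t distribution with 42 degrees of freedom and noncentrality margin / 1.869.

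| Margin (ESS points) | One-sided 5% | One-sided 2.5% |
|---|---|---|
| 2 | 28% | 18% |
| 3 | 47% | 35% |
| 4 | 68% | 55% |
| 5 | 84% | 74% |
| Margin for 80% power | 4.72 | 5.36 |

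Against the cited modafinil change from baseline, 4.72 / 5.3 = 89% and 5.36 / 5.3 = 101%.

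**3. How far the responder power depends on the 80% rate.** With equal rates p in both arms the variance is largest at p = 0.5. There the standard error is √(2 × 0.5 × 0.5 / 22) = 0.1508, and power at one-sided 5% is Φ(0.30 / 0.1508 − 1.645) = Φ(0.345) = 63.5%. That is the floor by the normal approximation. Intermediate rates of 70% and 60% give 70% and 65%.

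**The case against.** The best defence is that the sample-size paragraph, under the heading Statistical Analysis and in the future tense, does name the non-inferiority analysis: the 25% responder comparison. On that reading the power, the limit and the test agree, and the adjacent sentences make plain which comparison is powered. The analysis paragraph's list of categorical outcomes is also introduced as including the PGI-C proportions, so it need not be exhaustive. This has weight: the documents do not settle that the t-test is the intended test. A reader might infer that the trial's non-inferiority test is simply underpowered, but the documents do not support that, because with no ESS margin the t-test has no single power. What the defence does not remove is that the analysis paragraph ties non-inferiority to the t-test and never mentions the 25% responder.

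The missing alpha is mainly a reporting gap. The cited calculator and method point to how the figure was obtained, and one-sided 5% is usable if prespecified. The 70% at one-sided 2.5% shows what the omission is worth; it does not describe a level that the plan claims.

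A reader might also infer that the 80% responder rate is contradicted by the paragraph's own mean of 5.3 and SD of 6.2. It is not. No baseline ESS is given, and the two figures are not one data set: the mean is a weighted average over three trials, and the SD carries a single citation and is attached to the amphetamine calculation. A normal model, Φ((5.3 − 0.25 × baseline) / 6.2), gives 64.5%, 58.3% and 51.9% responders at assumed baselines of 12, 16 and 20. But a bounded beta model on an assumed 0–24 scale gives 85.3% and 79.6% at baselines of 8 and 9. The answer depends on the assumed baseline and distribution, and the mean and SD alone do not exclude 80%.

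**Conclusion.** The two paragraphs of the Statistical Analysis section disagree on the non-inferiority analysis and must be reconciled. The 80% is correct for the responder comparison at one-sided 5% and 80% responders, and it is not the power of the t-test. That mismatch needs no assumed baseline or distribution.

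Its size, if the t-test is the intended test, depends on the margin chosen: power runs from 28% at 2 points to 84% at 5 points at one-sided 5%. A margin that 22 per group can support with 80% power is close to the whole cited modafinil change from baseline. These figures rest on SD 6.2 in both arms and no true difference.

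The unsourced responder rate is a secondary caveat. If the true common rate is below 80%, power at one-sided 5% falls, but to no less than about 63.5%. Nothing here shows that 80% is wrong.

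**What to change.** Keep 22 per group and make these changes before any unblinded comparison.

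1. Name one non-inferiority test in both paragraphs.
   - *If it is the responder comparison:* add the 25% ESS responder to the analysis paragraph with the 30% limit, one-sided 5% alpha and the matching rule (the two-sided 90% confidence interval for the difference in proportions must exclude a deficit of 30 percentage points or more). Present the t-test as a comparison of means with no non-inferiority claim.
   - *If it is the t-test:* prespecify and justify a margin in ESS points, state the confidence-interval rule, and replace the 80% with the power for that margin from the table above. Label the responder power as belonging to a different comparison, or drop it.
2. State alpha and sidedness wherever power or a test is described.
3. Give a source for the 80% responder rate, or add a sentence showing how the power changes at lower rates.

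There is no cost in patients, and the 30% limit need not change. This is more than wording, however: naming the test settles an analysis choice that is now open, and the stated power may become less favourable. Under the t-test option the text would show openly that the trial can support only a wide ESS margin with 80% power.

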Medications will be provided initially as: modafinil 100 mg qam and amphetamine salts 10 mg qam. For patients reporting difficulty awakening at baseline, the first dose will be taken 1 hour before planned awakening, whenever possible. For patients without difficulty awakening at baseline, first dose will be taken upon awakening. Patients will be advised to increase dosage once a week with the following schedule: week 2, 1 pill qam and 1 qnoon; week 3: 2 pills qam and 1 qnoon; week 4 and beyond: 2 pills qam and 2 pills qnoon. Patients will be instructed not to titrate further once they feel symptoms are well-controlled and to reduce dosage one step in the case of mild to moderate side effects. In the case of severe side effects, participants will be instructed to discontinue treatment but will still continue all remaining study visits and questionnaires. This titration will allow participants to reach doses of modafinil as high as 200 mg bid, the maximum FDA approved dose of modafinil in the treatment of narcolepsy. Participants will reach a maximum dose of amphetamine salts of 20 mg bid. Although the maximum FDA approved dose of amphetamine salts for treatment of narcolepsy is higher at 60 mg/day, adverse events are dose-related and higher doses do not necessarily convey additional benefit (33); in clinical practice, finding the lowest effective amphetamine dosage and maintaining this dosage as long as it is effective is a practical component of the management of both the risk of side effects and the problem of tolerance that occurs in 1/3rd patient with narcolepsy treated with amphetamines (34).

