This study will recruit up to 55 participants, with a sample size target of 44 participants who complete participation in the 12 week medication trial. Participants will be newly diagnosed, medication-naïve individuals, or formerly diagnosed, free of wake-promoting medication or willing to discontinue current wake-promoting medication with diagnoses of: narcolepsy type 2 or idiopathic hypersomnia.

Inclusion criteria will be: 1) narcolepsy type 2 or idiopathic hypersomnia; 2) age 18-65; 3) informed consent.

Exclusion criteria will be: 1) contraindication to modafinil or amphetamine salts (history of left ventricular hypertrophy, mitral valve prolapse, other cardiac structural abnormalities, severe cardiovascular disease, unstable angina, myocardial infarction, cardiomyopathy, severe arrhythmias, uncontrolled hypertension, severe hepatic impairment, substance abuse history, psychosis, glaucoma, Tourette's syndrome, and epilepsy); 2) obstructive sleep apnea (AHI > 15); 3) severe periodic limb movements of sleep with arousals (PLM arousal index > 30); 4) allergy to either of the study drugs; and 4) pregnancy or breastfeeding.

Participants who withdraw from study medication will be invited to complete remaining questionnaires/study visits.

Visit Schedule

Visit 1: Enrollment: After reviewing information about the study and confirming participation, subjects will answer questions about their sleep disorder and the symptoms experienced. This visit is expected to last about one hour. If participants are suspected of having a diagnosis of narcolepsy type 2 or idiopathic hypersomnia and have never had an overnight polysomnogram (PSG) and next-day MSLT, they will be scheduled for an

additional study visit to complete a PSG and MSLT before visit 3. If participants already have a confirmed diagnosis of narcolepsy type 2 or idiopathic hypersomnia and are taking certain stimulant medications they will be asked to wean off of this medication before and during the study. After weaning off of medicines, the participant will be given a four-week supply of one of the two study medications. The medication will be provided will be assigned randomly, the participant and the doctor will not be told which of the two study medications are given.

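### Non-inferiority on ESS change rests on an unadjusted t-test with LOCF and no missing-data sensitivity analysis; baseline adjustment is nearly free, and a repeated-measures model avoids the LOCF bias if loss is at random

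*Combined protocol and SAP*

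**What the plan says.** The Statistical Analysis section sets the missing-data rule: "Intention-to-treat analyses will be performed, using last observation carried forward in the event of participant drop-out". It continues: "The change in ESS at week 12 from baseline will be compared between the two treatment groups via t-test", with an unequal-variance version if needed, judged as non-inferiority. It names no covariate, repeated-measures model or missing-data sensitivity analysis for this comparison. Baseline ESS appears as a predictor only in the exploratory within-drug logistic models.

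Other parts of the protocol bear on this:

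- Study Design & Methods schedules ESS at baseline and weeks 4, 8 and 12. Weeks 4 and 8 are collected remotely. Baseline and week 12 are face to face, and virtual under the pandemic arrangements.
- The dosing paragraph ends its titration schedule with "week 4 and beyond: 2 pills qam and 2 pills qnoon", but tells patients to stop stepping up once symptoms are controlled. It also refers to "the problem of tolerance that occurs in 1/3rd patient with narcolepsy treated with amphetamines".
- Stopping drug is not the same as leaving the study. After severe side effects, "participants will be instructed to discontinue treatment but will still continue all remaining study visits and questionnaires". Participant Selection adds: "Participants who withdraw from study medication will be invited to complete remaining questionnaires/study visits".
- On numbers: "This study will recruit up to 55 participants, with a sample size target of 44 participants who complete participation".
- The only stated non-inferiority limit is 30 percentage points on ESS responders. No margin in ESS points is given.

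**The concern.** With about 22 patients per arm, precision is scarce. The plan uses baseline ESS only by subtraction, which is usually less efficient than adjusting for it.

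LOCF is the more substantive matter. For someone lost before week 4 it enters, on the natural reading, a change of zero. For someone lost later it enters a week-4 or week-8 score as if it were week 12. A patient who takes every titration step on time has the week-4 assessment about a week after the last step; the interval is longer for those who stop titrating earlier. In a superiority trial, shrinking a difference is usually conservative. In a non-inferiority trial it makes a drug that is truly worse look acceptable. The chance of declaring non-inferiority then depends partly on how many people leave and when, not only on the drugs, and nothing planned would show how much.

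**Working it through.** **The plan's own figures.** The 82.8% power reproduces as a within-arm (one-sample) t-test: n = 22, two-sided 5%, effect 4/6.2 = 0.645 gives 82.3%, or 82.8% with the effect rounded to 0.65. The responder figure reproduces at one-sided 5%: (1.645 + 0.842)² × 2 × 0.8 × 0.2 / 0.30² = 22 per arm. Neither is the power of the planned between-arm t-test on mean change. I use one-sided 5% below because the documents state no alpha and this one reproduces the responder figure.

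**Inputs.** From the documents: 22 per arm, SD of change 6.2, modafinil change 5.3 points. Assumed: correlation r between baseline and week-12 ESS of 0.3 to 0.7; ratio k of week-12 SD to baseline SD of 1 or 1.5; ESS margins of 2.65 (half of 5.3) and 4 points (the planning reduction); onset and loss patterns as below.

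**(a) Baseline adjustment.** Variance of ANCOVA relative to the change score, including the cost of estimating the slope:

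ratio = [k²(1 − r²) / (1 + k² − 2rk)] × (1 + 1/40)

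| r | k = 1 | k = 1.5 |
|---|---|---|
| 0.3 | 0.650 × 1.025 = 0.666 | 0.871 × 1.025 = 0.893 |
| 0.5 | 0.750 × 1.025 = 0.769 | 0.964 × 1.025 = 0.988 |
| 0.7 | 0.850 × 1.025 = 0.871 | 0.998 × 1.025 = 1.023 |

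The t-test has standard error 6.2 × √(2/22) = 1.87 and a 90% CI half-width of 1.682 × 1.87 = 3.14 points. With ANCOVA the half-width is 2.57-2.94 (k = 1) or 2.97-3.18 (k = 1.5). Illustrative power with equal drugs (noncentral t):

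| Margin | t-test | ANCOVA, k = 1 | ANCOVA, k = 1.5 |
|---|---|---|---|
| 2.65 | 40.1% | 44.0-52.5% | 39.5-43.3% |
| 4 | 67.7% | 72.9-82.5% | 66.9-72.0% |

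The worst case loses under one power point.

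**(b) LOCF bias.** Spread loss L evenly before weeks 4, 8 and 12, and let f4 and f8 be the shares of the week-12 effect present at weeks 4 and 8. The arm's mean effect shrinks by s = (L/3)(3 − f4 − f8).

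- L = 10%: f = 66/91% gives s = 0.0333 × 1.43 = 0.048; f = 80/95% gives 0.0333 × 1.25 = 0.042.
- L = 20%: 0.095 and 0.083.

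With the same s in both arms, the LOCF difference is (1 − s) times the true one. At a true deficit of 2.65 the bias is 0.11-0.25 points. If the drugs are equal it is zero.

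With unequal loss the sign varies. For equal drugs, 66/91% onset, and 10% modafinil against 20% amphetamine loss, the bias is 5.3 × (0.0953 − 0.0477) = 0.25 points against amphetamine. Suppose instead that loss is 20% in both arms and the amphetamine effect at weeks 4/8 is 125/110% to 175/140% of its week-12 value. Then s for amphetamine is 0.043 to −0.010, and the bias is 5.3 × (0.0953 − 0.0433) = 0.28 to 5.3 × (0.0953 + 0.0100) = 0.56 points in its favour.

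Simulated false non-inferiority (true deficit equal to the margin, 40,000 trials per cell, 22 or 27 per arm, r = 0.5, k = 1):

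| Loss in each arm | Both effects rising | Amphetamine waning |
|---|---|---|
| 0% | about 5% | about 5% |
| 10% | about 5.5-6.5% | about 6-7% |
| 20% | about 6.5-8% | about 7.5-9% |

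On the stated 30-point responder margin (80% v 50%, unpooled Wald test, exact enumeration, both rates multiplied by 1 − s), the rates are 4.9-5.1% with no loss, 6.2-6.5% at 10% and 7.5-8.4% at 20%.

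**(c) The alternative.** Simulated at margin 2.65 with 27 per arm, a repeated-measures model with unstructured covariance gave 4.1-5.2% when loss was at random (LOCF in the same runs 5.2-9.8%). When loss depended on the unseen week-12 score it gave 5.5-6.3% (LOCF 5.7-8.4%). The simulated degrees of freedom were week-12 completers minus 3, not Kenward-Roger. ANCOVA on LOCF data does not help: with 36% v 12% loss the bias was 0.74 points, against 0.75 for the t-test.

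**The case against.** The unadjusted t-test on change is valid under randomisation. A reader might infer that it is an error, but it is only less efficient, and at k = 1.5 the gain almost vanishes. The ESS-point power figures also rest on margins that the plan does not contain, and the gain does not reach the responder test, the only one with a stated limit. All of this stands.

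The LOCF bias is modest: 0.11-0.25 points at a true deficit of 2.65, against a half-width of 3.14. Patients who stop drug are kept or invited to continue, and weeks 4 and 8 are remote, so true loss may be small. The 20% figure is (55 − 44)/55, a ceiling on recruitment that includes people withdrawn before dosing after a negative sleep study; it is not a forecast of drop-out. This stands as a limit on size. It does not reach people who leave the study altogether.

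A reader might also infer from the tolerance remark that the amphetamine effect fades within 12 weeks. The dosing paragraph gives no time course, so the waning column is hypothetical.

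Finally, the replacement has limits. If loss is not at random, its error range overlaps that of LOCF. If lost amphetamine patients were 2-4 points worse than predicted, the contrast would be off by 0.2-0.4 points at 10% loss and 0.4-0.8 at 20%, which can exceed the LOCF bias. A model of post-baseline scores alone also learns nothing from patients who have none: with the loss pattern above, (0.20/3) × 55, or about 4 people, despite the intention-to-treat aim. Both points stand, and the fix has to meet them.

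**Conclusion.** The concern holds as a recommended improvement. Baseline adjustment is nearly free: variance changes by −33% to −13% with equal SDs, and by −11% to +2% if the week-12 SD is 1.5 times baseline, for r of 0.3 to 0.7. LOCF lets the amount and timing of loss influence the primary conclusion, and no planned analysis would reveal it. Under the assumed patterns, false non-inferiority rises from 5% to about 5.5-6.5% at 10% loss and 6.5-8% at 20%, and to about 9% only if the amphetamine effect wanes.

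The documents do not support saying that LOCF always favours non-inferiority. That needs balanced loss with a rising effect, or early scores that overstate amphetamine. Unequal loss can push either way, and with equal loss and equal trajectories the bias is zero. Its actual size cannot be known from the documents.

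**What to change.** Before unblinding, replace the t-test and LOCF sentences along these lines:

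- **Primary analysis.** A mixed model for repeated measures on ESS at weeks 4, 8 and 12, with treatment, visit, treatment-by-visit, baseline ESS and baseline-by-visit, unstructured covariance and small-sample (for example Kenward-Roger) degrees of freedom. Use every observed score, including those after stopping study drug. Report the week-12 contrast with its confidence interval.
- **All randomised patients.** Include those with no post-baseline ESS by multiple imputation under the same model, or by a constrained model with baseline as an outcome.
- **Responders.** Classify them for the 30-point limit from the same imputations.
- **Sensitivity.** Make the imputed week-12 scores of lost amphetamine patients worse in steps until the non-inferiority conclusion changes, and report that step. Keep LOCF only as a secondary check.
- **At minimum.** Use ANCOVA of week-12 ESS on baseline ESS and treatment, noting that on LOCF data it leaves the LOCF bias in place.

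The cost is wording, some programming, one degree of freedom and about 2.5% of variance for the slope. No new data are needed. The main downside is that the model removes the LOCF bias only if loss is missing at random, which is why the delta analysis belongs with it.

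### The non-inferiority conclusion rests on intention-to-treat with last observation carried forward alone; if stopping drug is similar in both arms or commoner on the better drug, this can favour a drug that works less well while taken

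*Combined protocol and SAP*

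**What the plan says.** The Statistical Analysis section compares week-12 change in Epworth score (ESS) between arms by t-test and says it "will be evaluated on a hypothesis of non-inferiority". On the analysis set and missing data it says only: "Intention-to-treat analyses will be performed, using last observation carried forward in the event of participant drop-out". It does not say whether drop-out means stopping drug or leaving follow-up.

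Stopping drug and staying under observation is provided for. For severe side effects, Study Design & Methods says "participants will be instructed to discontinue treatment but will still continue all remaining study visits and questionnaires". Participant Selection invites those who withdraw from medication to complete what remains of the questionnaires and visits. It also allows up to 55 recruits, "with a sample size target of 44 participants who complete participation".

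The only non-inferiority limit is on responders, defined by a 25% fall in ESS: "Assuming 80% of participants meet this threshold, 22 participants per group will provide 80% power to a non-inferiority limit of 30" percent. No limit is given in ESS points, and no alpha is given.

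Appendix 1 schedules the ESS at every visit and a count of returned drug at Visits 3, 4 and 5. An adherence-based analysis set could therefore be built, but none is defined. The exploratory analyses at weeks 4 and 8 concern time to symptom control, not adherence.

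**The concern.** In a superiority trial, intention-to-treat usually errs on the safe side, because people off drug make the arms look alike and a real difference becomes harder to show. In a non-inferiority trial, looking alike is the result being claimed, so the same dilution can work in favour of the claim. A drug that is worse by the full limit while taken may pass because enough people in both arms were not taking anything.

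A false declaration of non-inferiority is the costly error here, since the trial is meant to inform the choice between the two drugs. With about 22 per arm, a few people off drug can matter. A single analysis, with drop-out undefined, gives the reader no means of seeing whether this happened.

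**Working it through.** **Inputs from the documents.** Responder rate 80%, limit 30 percentage points, 22 per arm, 80% power (Statistical Analysis); 1:1 allocation (Study Design & Methods); up to 55 recruited for 44 completers (Participant Selection).

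**Assumptions, because the documents give no figure.** Alpha; the share stopping drug in each arm (range 0% to 30%); the response of those off drug, q (range 0% to 40%, the same in both arms).

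**Step 1: reproduce the planned size.** n per arm = (z_alpha + z_power)² × [p(1−p) + p(1−p)] / limit².
- One-sided 5%: (1.645 + 0.842)² × 0.32 / 0.09 = 21.98, so 22 per arm, as stated.
- One-sided 2.5%: (1.960 + 0.842)² × 0.32 / 0.09 = 27.9, so 28 per arm.

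The stated 22 therefore implies one-sided 5%, which is used below.

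**Step 2: dilute the response.** Set the on-drug rates exactly at the limit: 80% on the better drug, 50% on the worse. With a fraction d stopping in an arm, the observed rate is (1−d) × p_on + d × q. With equal d, q cancels and the difference is (1−d) × 30 points. At d = 20% and q = 10%, the rates are 0.8 × 0.80 + 0.2 × 0.10 = 0.66 and 0.8 × 0.50 + 0.2 × 0.10 = 0.42, a difference of 24 points.

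**Step 3: chance of declaring non-inferiority.** The rule is: observed difference + 1.645 × unpooled standard error < 30 points. Normal approximation for the example: SE = √(0.66 × 0.34/22 + 0.42 × 0.58/22) = 0.146; (0.30 − 0.24)/0.146 − 1.645 = −1.23; probability 10.9%. Exact binomial enumeration of the same rule gives 12.0%. For equal stopping:

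| Stopping in each arm | Difference (points) | Normal approx., 22 per arm | Exact, 22 per arm |
|---|---|---|---|
| 0% | 30 | 5.0% | 5.1% |
| 10% | 27 | 7.6% | about 8% |
| 20% | 24 | 10.9% | about 12% |
| 30% | 21 | 15.1% | about 17% |

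The results barely move as q goes from 0% to 40%. With 27 per arm (about half of 55) the exact figures at 20% and 30% stopping are about 13% and 19%.

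**Step 4: unequal stopping (exact, 22 per arm).**
- Better drug stopped more (30% versus 10%), q = 10%: rates 0.59 and 0.46, difference 13 points, chance about 34%.
- Worse drug stopped more (30% versus 10%): at q = 0 the rates are 0.72 and 0.35, difference 37 points, chance 1.8%. At q = 40% they are 0.76 and 0.47, difference 29 points, chance 6.0%.

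**Step 5: drugs truly equal.** At 80% in both arms and 22 per arm, exact power is 82%. With 20% stopping it falls to 69% to 73% for q from 0% to 40%.

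**Step 6: cost of a per-protocol set.** Excluding 20% of 22 leaves 17.6, about 18 per arm. Power = Φ(0.30/√(0.32/18) − 1.645) = Φ(2.25 − 1.645) = 73%; exact, 74%.

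**The case against.** The strongest reply is that this is a pragmatic effectiveness trial. Following people after they stop drug suits a treatment-policy question, and for that question the 24-point difference in the example is the true effect, so passing is not an error. That stands as a reason to keep intention-to-treat as primary. It does not remove the need to show what happens on drug when the conclusion is non-inferiority.

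Four stronger readings are tempting, and the documents do not support them:

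- **That dilution always makes a worse drug easier to pass.** It depends on who stops. If the worse drug is stopped more often, the chance can stay near or fall below nominal (Step 4). If the drugs are equal, dilution costs power (Step 5).
- **That the plan expects 20% to stop drug.** The gap between 55 and 44 is 11/55 = 20%, but it is a ceiling on non-completion. It can also absorb people withdrawn after a negative sleep study (Visit Schedule, Visit 2), before any drug is dispensed. Conversely, those who stop drug may still complete. No stopping rate appears anywhere.
- **That the figures measure bias from carrying scores forward.** Carrying forward is not modelled here. A carried score from week 4 or 8 may be an on-drug one and need not pull the arms together. On the natural reading, it applies only to people who leave follow-up, and attended off-drug visits are used as observed; the plan just does not say so.
- **That non-inferiority should require both analyses to pass.** This would make a smaller subset selected by adherence decisive, and joint power could not exceed the lower of the two. In this trial that is a debatable trade-off, not a correction.

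**Conclusion.** The point holds as a conditional one. The plan supports a non-inferiority conclusion with a single analysis, although it provides for off-drug follow-up. If stopping is similar in both arms, or commoner on the better drug, a drug worse by the full 30 points while taken would pass more often than the nominal 5%: about 8%, 12% and 17% at 10%, 20% and 30% equal stopping.

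These figures rest on an inferred one-sided 5%, assumed stopping rates, equal off-drug response, and the on-drug effect as the quantity of interest. They are on the responder scale, because the planned t-test on ESS change has no limit in points; they illustrate the mechanism and do not estimate the error of the primary test. Shrinkage under equal stopping with similar off-drug scores applies to mean change as well. The direction can reverse, and a single analysis cannot show which case occurred. This is a cheap improvement to the plan, not a fault that invalidates the primary analysis.

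**What to change.** In the Statistical Analysis section:

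- Keep intention-to-treat as primary. State that the observed week-12 ESS is used whenever that visit was attended, on or off drug, and that a score is carried forward only when the week-12 value is missing. This also settles what drop-out means.
- Pre-specify a supportive per-protocol analysis: on assigned drug through week 12 by returned-drug count, an observed week-12 ESS, and no major eligibility deviation.
- Pre-specify a sensitivity analysis that does not carry scores forward, for example a repeated-measures model using the scheduled ESS scores.
- Report both beside the primary result, with the number stopping drug in each arm, and describe non-inferiority as robust only if they agree.

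The cost is wording and two further analyses of data already scheduled. The per-protocol set is smaller and not protected by randomisation. With about 18 per arm its power is about 73% to 74%, so disagreement may reflect a wide interval and should be read that way.
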